2.0 Enrollment/Randomization

The current study will be an open label study. Subjects will be enrolled among patients who are admitted with an acute coronary syndrome (unstable angina, non-STEMI) and who are being referred for coronary angiography and possible percutaneous coronary intervention. All study candidates must have received at least 300mg of clopidogrel loading dose since admission, or have been on clopidogrel 75mg daily for >5 days at time of enrollment.

Subjects will be enrolled before undergoing diagnostic angiography using written informed consent after screening for appropriate candidates. Patients will have the first study blood draw performed prior to coronary angiography. In case significant coronary disease is found and the patient proceeds with percutaneous coronary intervention, the patient will be randomized to either a TEG guided or LTA guided strategy. The subject will then be switched to prasugrel or continue on clopidogrel according to the results of the pre-cath TEG or LTA measurements. Patients in the TEG guided arm with high physical clot strength ($MA \geq 69$) will be assigned to prasugrel, whereas patients with lower clot strength ($MA < 69$) will continue on clopidogrel. This cutoff reflects the 50th percentile of clot strength based on data from a prior cohort of patients undergoing PCI and was determined as cutoff for ischemic risk in prior studies.

Patients in the LTA guided arm with high on treatment platelet reactivity to ADP ($PA > 42.9\%$) will be assigned to prasugrel, whereas patients with low on treatment platelet reactivity ($PA \leq 42.9\%$) will continue on clopidogrel. This value was determined as a significant cutoff for ischemic risk in prior studies. If the decision is made to proceed with percutaneous revascularization, patients assigned to remain on clopidogrel will receive 300mg clopidogrel loading dose in the cath lab, and then remain on 75mg po daily. Patients assigned to prasugrel will receive 60mg po loading dose, and then remain on 10mg po daily.

Telephone follow-up will be conducted after 6 months to assess for ischemic and bleeding events.

The enrollment and study process is depicted in a Fig 1.

We plan on enrolling 100 subjects, with 50 subjects randomized to each arm:

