3.0 Study Procedures

After signing of informed consent, patients are asked to fill out a short questionnaire regarding demographics, risk factors, family history and dietary history that will take 5 minutes to complete.

Venous blood will be collected through peripheral venous puncture (~ 20ml) prior to cardiac catheterization and again 16-24 hours post PCI.

Thrombelastography measurements and light transmittance aggregometry will be performed using several agonists on both occasions. The remaining buffy coat will be collected and frozen at -80°C for DNA extraction and analysis. Analysis of candidate genes involved in metabolism of thienopyridines, platelet aggregation, and coagulation will be performed.

Patient records from the Indiana Network for Patient Care (INPC) will be accessed for analysis of cardiovascular outcomes.

Data that will be collected for database analyses includes the following (not exclusive):

Demographics	Age Gender Weight Height
Race/ Ethnicity	Self reported
Risk factors/Co-morbidities	Diabetes mellitus Hypertension Hyperlipidemia PVD COPD/Asthma Renal failure/Dialysis Smoking history Valvular disease Hx of arrhythmias
Nutritional History	Caffeine consumption Alcohol use
Medications	Current medication list
History of Present Illness	Reason for referral for cardiac cath
Laboratory	Most recent laboratory data prior to stress test will be obtained from INPC to include: Cardiac markers (troponin, CK, CKMB) Complete blood count Basic metabolic profile Liver function tests (if available) Lipid profile
Electrocardiogram	As per standard of care
Cardiac catheterization	Cines/Images from cardiac catheterizations performed

4.0 Reporting of Adverse Events or Unanticipated Problems involving Risk to Participants or Others

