4.5 Study Withdrawal/Discontinuation

Participants may withdraw from the participation in the study at any time. This requires a written request to the principal investigator.

5 Statistical Considerations

Sample size calculation was performed assuming an estimated prevalence of 50% of MA ≥ 69 in the general patient population with ACS on clopidogrel referred for cardiac catheterization according to previous studies. It was assumed that switching to prasugrel would reduce the maximal clot strength in 60% of these patients with baseline MA ≥ 69 resulting in 20% prevalence of high tensile clot strength. Assuming a power of 0.8 and alpha 0.05 with a loss of 5% of follow-up, a sample size of 50 in each arm and a total sample size of n=100 was calculated accordingly.

6 Privacy/Confidentiality Issues

All information will be collected and kept on a customized database on computers of the investigators and on a secure network server at the Krannert Institute of Cardiology. Access to the database is password protected and computers will be kept in locked offices at the Krannert Institute and Wishard Hospital. Access to the offices housing the information is only available via keys possessed by the investigators. Only the listed investigators of the study will have access to review information and to analyze data. Data sent for analysis will be de-identified. The names of the patients will not be revealed if the results of this study lead to a publication.

The genetic information found through the course of the study will not be revealed to the study participants or their family members.

Blood samples are stored in a secured biospecimen storage facility that has secured access. Biospecimens are deidentified and do not allow identification of patients.

7 Follow-up and Record Retention

The study will last for at least 6 months after enrollment of the last study subject. Records and samples will be kept as required by the IRB and federal legislation and until completion of all study related analyses.

D. FACILITIES AVAILABLE

The cardiac catheterization laboratories at Wishard Hospital and Methodist Hospital will be used as study locations as required for the clinical care of the patients. Standard hospital care will be provided.

Laboratory analyses including platelet studies, thrombelastography, as well as DNA analysis will be performed in the laboratories of the Division of Clinical Pharmacology, Indiana University School of Medicine.

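### Section 2.0 names no stratification factor; balancing on pre-cath MA ≥ 69, and adjusting for it, would be a cheap gain in precision for the primary comparison

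*Protocol*

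**What the plan says.** Protocol Section 2.0 has the first study sample taken before angiography. If PCI follows, "the patient will be randomized to either a TEG guided or LTA guided strategy". The allocation is equal: "We plan on enrolling 100 subjects, with 50 subjects randomized to each arm". No stratification factor, blocking or sequence method is named, and Fig 1, which depicts the process, is not shown.

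The drug then follows the assigned test. In the TEG arm MA ≥ 69 leads to prasugrel; in the LTA arm PA > 42.9% does. Under Section 3.0 blood is drawn "prior to cardiac catheterization and again 16-24 hours post PCI", and both TEG and LTA are run on each sample, so every patient in both arms has a baseline MA.

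The primary endpoint (Section B) is persistence of high clot strength 16-24 hours after reloading. Section 5 sizes the trial "assuming an estimated prevalence of 50% of MA ≥ 69 in the general patient population with ACS" and supposes that "switching to prasugrel would reduce the maximal clot strength in 60% of these patients", "resulting in 20% prevalence of high tensile clot strength".

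**The concern.** The endpoint is the baseline measurement repeated after treatment, and judged against the same MA cutoff of 69. When a baseline value predicts the endpoint that strongly, leaving its split between arms to chance adds variance that could be removed at little cost. With 50 per arm the chance gaps are not negligible.

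The allocation method is fixed in the protocol. A later analysis plan can adjust for baseline MA, but it cannot restore balance. What is at stake is precision on the primary comparison, most of all if the true difference is smaller than planned. That could happen, because LTA-arm patients with high platelet reactivity also receive prasugrel.

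**Working it through.** **Inputs.** From Section 5: baseline prevalence 50%, conversion on prasugrel 60%, resulting rate 20%, power 0.8, alpha 0.05 (taken as two-sided), loss 5%. From Section 2.0: 50 per arm. Evaluable per arm: 50 × 0.95 = 47.5, taken as 47.

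**1. The plan's own sample size.** For 50% versus 20%, mean 0.35:
- n = [1.96√(2 × 0.35 × 0.65) + 0.842√(0.25 + 0.16)]² / 0.30² = 38.5, so 39 per arm.
- With continuity correction: 45. Allowing for loss: 45/0.95 = 47.4, so 48.

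This is within 2 of the stated 50, so the figure reproduces.

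**2. What the planning model says about strata.** 0.50 × 0.40 = 0.20 leaves nothing for baseline-low patients. Every follow-up event comes from the baseline-high half. In the comparator, held at 50%, all baseline-high patients stay high; in the TEG arm 40% of them do.

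**3. Chance imbalance.** With two independent Binomial(50, 0.5) counts, the SD of the difference in baseline-high share is √(2 × 0.25/50) = 10 points. Exact probabilities of a gap of at least:
- 5 patients (10 points): 36.8%
- 8 patients (16 points): 13.3%
- 10 patients (20 points): 5.7%

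A gap g split evenly about the mean moves the estimated difference by (g/2)(1.00 + 0.40) = 0.7g. A 10-point gap therefore moves it by 7 points, against a planned 30.

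**4. SD of the arm difference, planning model, 47 per arm.**
- Simple: √[(0.5 × 0.5 + 0.2 × 0.8)/47] = √(0.41/47) = 9.3 points.
- Stratified, three variance terms. Outcome variation among TEG-arm baseline-high patients: 0.5 × 0.4 × 0.6/47 = 0.12/47 = 0.00255. The share of baseline-high patients in the whole trial, which stays random: 0.6² × 0.125/47 = 0.00096. An odd patient in a stratum: 0.7² × 0.5/47² = 0.00011. Sum 0.00362, SD 6.0 points.

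Simulation agrees on both. The mean estimate is 30 points either way.

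**5. Power, separating allocation from analysis (simulation).**

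| Case | Simple, unadjusted | Stratified, unadjusted | Simple + CMH | Stratified + CMH |
|---|---|---|---|---|
| Planning model, 47 per arm | 0.88 | 0.96 | about 1.00 | about 1.00 |
| Assumed case, 50 per arm | 0.52 | 0.52 | 0.74 | 0.745 to 0.78 |

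The assumed case puts 40% of the LTA arm on prasugrel, with 60% of baseline-high patients on prasugrel clearing and no other crossing of 69. The LTA-arm rate is then 0.5 × (1 − 0.4 × 0.6) = 0.38, against 0.20. The 40% is not in the protocol. In the last cell, 0.745 lets the number of baseline-high patients enrolled vary, and the top of the range fixes it at 25 per arm. Stratified randomisation does not fix that number, so the lower figure is the fairer one.

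The gain fades if clopidogrel patients cross 69 in both directions. With upward crossing at the same rate on either drug, 15% crossing gives about 0.29 unadjusted and 0.34 with CMH; 25% gives 0.19 and 0.20.

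**6. Type I error.** Simple and unadjusted: 4.9 to 5.2% over three null cases. CMH: 4.7 to 5.1% under either allocation. Stratified but analysed unadjusted: 0.2 to 2.5%, that is, conservative.

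**The case against.** The strongest reply is that adjustment does nearly all the work. In the assumed case, about 23 points of power come from CMH under simple randomisation, and stratified allocation adds between almost nothing and 4 more. Whether to adjust is usually settled in the analysis plan, which is not shown, and nothing in the protocol prevents it. This stands, and it limits the point to a modest one. What remains at protocol level is balance on the baseline value of the endpoint.

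The other replies correct stronger readings that a reader might draw:
- *That the protocol chose unstratified randomisation.* It is silent on method, and its figure is not available.
- *That an arm difference could be an artefact of unequal high-MA counts.* Over repeated trials the estimate is unbiased, and the unadjusted test's standard error already carries this variation.
- *That stratifying lifts power from 0.52 to about 0.77.* That comparison changes allocation and analysis together, and rests on the assumed 40%. Under the protocol's own assumptions the unadjusted test has about 0.88 power, above the planned 0.80.
- *That baseline MA sets prasugrel use in both arms.* It does so only in the TEG arm. In the LTA arm PA > 42.9% decides, so balancing MA would not control that arm's share, or its part in the bleeding and ischemic comparisons.
- *That baseline MA settles the endpoint.* It does so for baseline-low patients and the planned comparator, but 60% of switched baseline-high patients are assumed to convert.

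**Conclusion.** The point holds as a cheap improvement. No stratification factor is named, although the obvious one is sampled in everyone before allocation and carries all primary events in the planning model. The cost of leaving it out is an SD of about 9.3 rather than 6.0 points under that model, and sizeable chance gaps in baseline MA.

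The SD figures rest on the planning model's premise that baseline-low patients never become high and that no comparator patient clears. If MA often crosses 69 on clopidogrel in both directions, baseline MA predicts less and the gain falls to almost nothing near 25% crossing. The protocol gives no figure for such crossing, so the true gain lies somewhere between these cases.

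**What to change.** - **Section 2.0:** state the randomisation method: 1:1, in permuted blocks of varying size, within pre-cath MA ≥ 69 versus < 69.
- **Section 5:** state that the primary comparison is stratified by, or adjusted for, the same factor, for example a CMH test with a stratum-weighted risk difference. This part is needed, because stratified allocation followed by an unadjusted test is conservative.
- **Late readings:** if MA is not available in time, randomise without it and adjust in the analysis.

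The cost is two allocation lists and a sentence or two in each section. There are two small downsides. The MA reading must be ready before allocation for all patients, whereas now it is needed at once only in the TEG arm. Blocks within known strata are also slightly easier to predict in an open-label trial, which is why block sizes should vary. If the sponsor prefers not to stratify, prespecifying the adjustment alone recovers most of the power.

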3.0 Study Procedures

After signing of informed consent, patients are asked to fill out a short questionnaire regarding demographics, risk factors, family history and dietary history that will take 5 minutes to complete.

Venous blood will be collected through peripheral venous puncture (~ 20ml) prior to cardiac catheterization and again 16-24 hours post PCI.

Thrombelastography measurements and light transmittance aggregometry will be performed using several agonists on both occasions. The remaining buffy coat will be collected and frozen at -80°C for DNA extraction and analysis. Analysis of candidate genes involved in metabolism of thienopyridines, platelet aggregation, and coagulation will be performed.

Patient records from the Indiana Network for Patient Care (INPC) will be accessed for analysis of cardiovascular outcomes.

Data that will be collected for database analyses includes the following (not exclusive):

Demographics	Age Gender Weight Height
Race/ Ethnicity	Self reported
Risk factors/Co-morbidities	Diabetes mellitus Hypertension Hyperlipidemia PVD COPD/Asthma Renal failure/Dialysis Smoking history Valvular disease Hx of arrhythmias
Nutritional History	Caffeine consumption Alcohol use
Medications	Current medication list
History of Present Illness	Reason for referral for cardiac cath
Laboratory	Most recent laboratory data prior to stress test will be obtained from INPC to include: Cardiac markers (troponin, CK, CKMB) Complete blood count Basic metabolic profile Liver function tests (if available) Lipid profile
Electrocardiogram	As per standard of care
Cardiac catheterization	Cines/Images from cardiac catheterizations performed

4.0 Reporting of Adverse Events or Unanticipated Problems involving Risk to Participants or Others

4.1 Data Safety Monitoring Board

A data safety monitoring board consisting of two physicians not directly involved with the study will monitor the progress of the study at least annually.

4.2. Reporting mechanisms for adverse events to the IRB, FDA, NIH.

The principal investigator and study coordinator will review the clinical course for immediate adverse events directly related to the study procedure. Unanticipated serious adverse events as defined below or loss of anonymity will be reported to the IRB within 10 days after discovery in writing. Anticipated adverse events of coronary interventions will be reported during continuing annual review to the IRB.

4.3. Plan for unanticipated AE reporting

Unanticipated serious adverse events must be reported to the IRB within 10 days of discovery. Unanticipated serious adverse events are events (including adverse events, injuries, side effects during a study) that caused harm to one or more subjects or others, or placed one or more subjects or others at increased risk of harm, **AND** were unexpected (the frequency or severity of the event is not accurately reflected in the informed consent document for the cardiac catheterization or is inconsistent with available literature, e.g. drug brochure, protocol) , **AND** were related (e.g. > 51% chance) to the research procedures, **AND** require revision to the informed consent document.

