Although increased P₂Y₁₂ receptor inhibition with prasugrel is more efficient in reducing ischemic events than clopidogrel, it also carries an increased risk for significant bleeding. Personalized treatment approaches should ideally be able to identify patients at need for higher or lower intensity of platelet P₂Y₁₂ inhibition in an attempt to optimize the risk/benefit ratio for each patient. However, currently only one study prospectively compared a personalized dosing approach of clopidogrel vs. standard dosing in 162 patients prior to coronary stenting [9].

In addition to the currently available antiplatelet drugs that inhibit ADP mediated platelet aggregation by inhibiting P₂Y₁₂, several oral thrombin receptor protease-activated receptor-1 (PAR-1) inhibitors (platelet thrombin receptor) have been developed. Two oral PAR-1 inhibitors have completed phase 2 clinical trials and the eventual addition of these drugs to standard dual antiplatelet therapy may in the future further increase bleeding risk for patients on several antiplatelet drugs. Theoretically, thrombelastography may provide an ideal methodology to identify patients at highest risk for thrombin mediated ischemic events or identify patients at risk of bleeding. In the surgical field, thrombelastography has been used successfully to predict postoperative bleeding risk and guide post surgical and trauma related transfusion requirements.

Currently controversy exists as to the optimal method to identify patients at risk for ischemic events after coronary interventions and several point of care assays measuring platelet inhibition are currently in use in large prospective clinical trials. These currently employed methods focus on the specific amount of ADP mediated platelet aggregation measured ex-vivo to guide risk prediction and intensity of P₂Y₁₂ inhibition by either dose adjustment of clopidogrel or switching therapy to prasugrel. Therefore, as a control group we will include a group of patients which will be assigned to prasugrel or clopidogrel therapy based on LTA measurements pre-cath using a cutoff that has been validated as a predictor of ischemic events in several other large studies [1].

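### Ten-day IRB reporting also requires that the event force a consent revision, so harmful, unexpected, related events needing no new consent wording wait for annual reporting

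*Protocol*

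**What the plan says.** Protocol Section 4.3 sets the prompt route: "Unanticipated serious adverse events must be reported to the IRB within 10 days of discovery". It then defines such events by four conditions, each joined to the next by AND:

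1. the event "caused harm to one or more subjects or others, or placed one or more subjects or others at increased risk of harm";
2. it was unexpected, either because "the frequency or severity of the event is not accurately reflected in the informed consent document for the cardiac catheterization" or because it conflicts with the literature, for which the drug brochure and the protocol are given as examples;
3. the events "were related (e.g. > 51% chance) to the research procedures";
4. they "require revision to the informed consent document".

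The other reporting provisions are these:

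- Section 4.2 takes over the Section 4.3 definition and adds loss of anonymity as the only other 10-day trigger. Anticipated events of coronary interventions go to the yearly continuing review.
- Section 4.4 sends all adverse events to the IRB once a year in writing.
- Section 4.1 has a two-physician board monitor progress at least annually, and states no event that would prompt an earlier look.

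**The concern.** The first three conditions describe the event: it did harm or raised risk, it was not foreseen, and the research probably caused it. Together they make the usual case for telling the IRB quickly. The fourth describes a possible response to the event. Because it is joined by AND, the study team's view that the consent form can stay as it is takes the event off the prompt route, however clearly the other three are met.

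The remedy for a harmful, unexpected, related event is not always new consent wording. It may be a change to study procedures or to laboratory handling. Under the written rule such an event is not reported within 10 days. At stake is how soon the IRB learns of harm in an open-label study that assigns patients to prasugrel or clopidogrel by a laboratory result.

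**Working it through.** No arithmetic on rates or sample size applies, and the Protocol gives no figure to reproduce. The check is a logical reading of Section 4.3 against every other route in Sections 4.1, 4.2 and 4.4.

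**Inputs.** Let H = harm or increased risk, U = unexpected, R = related, C = consent form must be revised. All four come from Section 4.3.

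**Rule as written.** 10-day report if H and U and R and C (or loss of anonymity, Section 4.2).

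**Rule without the fourth condition.** 10-day report if H and U and R (or loss of anonymity).

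**Difference.** Four yes/no conditions give 2 × 2 × 2 × 2 = 16 combinations. The written rule sends 1 of them to the 10-day route (all four met). The amended rule sends 2. The one combination that changes is H, U and R met with C not met.

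**Where that combination goes now.**

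| Route | Does it catch H, U, R without C? |
|---|---|
| 4.3, 10 days | No, C fails |
| 4.2, loss of anonymity, 10 days | No, unless anonymity was also lost |
| 4.2, anticipated events, annual review | No, the event is unexpected |
| 4.4, all adverse events, annual | Yes |
| 4.1, board | At its next look, required at least annually |

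Only the annual routes remain.

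**Size of the delay.** If annual reports are at most 12 months (365 days) apart, an event discovered just after one report waits up to 365 days instead of 10. The added delay is at most 365 − 10 = 355 days. This is an upper bound, since an event discovered shortly before a report waits far less.

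**What the fix leaves unchanged.** An event classed as expected fails U under both rules and goes to annual reporting under both.

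**The case against.** The best defence is that condition 4 is a triage judgement like the others. Relatedness and unexpectedness are also decided by the study team before the IRB sees anything, so the rule is not circular, and to call it so would be too strong. That stands. It does not rescue the condition, which can still exclude an event that meets the other three.

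A second defence is that conditions 2 and 4 overlap: an event missing from a consent form will often call for a change to one. This limits the number of events affected. But unexpectedness can also be shown by conflict with the literature, and the remedy need not be consent wording. If the overlap were complete, the clause would be redundant and could be deleted at no cost. If it is not, the clause excludes events that should be reported promptly.

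A third is that local IRB rules may prescribe this wording. They are not in the Protocol, so compliance cannot be judged and no breach is claimed.

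Three stronger readings are tempting, and the Protocol does not support them.

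- *Serious bleeding on prasugrel would go unreported because of this clause.* The Introduction says of prasugrel that "it also carries an increased risk for significant bleeding". Bleeding classed as expected for that reason fails condition 2, so deleting condition 4 would not move it. Nor would it go unreported, since Section 4.4 covers all adverse events.
- *Tying expectedness to the catheterization consent hides drug events.* That reference is one of two alternatives joined by *or*, and the other already names the drug brochure and the protocol. A drug event absent from the catheterization consent counts as unexpected on that ground alone, so the reference widens the route.
- *Only early events are looked at.* Section 4.2 says that the principal investigator and coordinator "will review the clinical course for immediate adverse events directly related to the study procedure", but not that they review nothing else. The 10-day clock runs from discovery with no time limit after the procedure, and Section 2.0 provides a 6-month telephone follow-up for ischemic and bleeding events.

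**Conclusion.** The point holds for one defined class: events that are harmful, unexpected and related but judged not to need a consent revision. For these the written rule replaces a 10-day report with annual reporting, a wait of up to about 12 months. No other stated route shortens that wait, and the board's required minimum is also annual.

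This rests on three assumptions: the rule is followed literally, annual reports are no more than 12 months apart, and no prompt route outside the Protocol applies. The heading of Section 4.2 names the FDA and NIH as well as the IRB, but the text sets out no prompt route to either. The frequency of such events cannot be derived from the document, and it may be low.

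This is a rule the Protocol states, not a detail left to another document. It concerns patient safety and does not affect the endpoints, randomization, sample size or analysis. It merits a short amendment.

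**What to change.** In Section 4.3, delete the fourth condition, so that harm or increased risk, unexpectedness and relatedness together trigger the 10-day report. Alternatively, keep the consent question but move it after the report, as a possible outcome of the IRB's review. Section 4.2 takes its definition from Section 4.3, so one edit serves both.

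The cost is a one-paragraph amendment and some additional prompt reports. With 100 patients these should be few, although that is a judgement and not a figure from the Protocol. Nothing in treatment assignment or analysis changes.
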